2.1 Objectives & Hypotheses

2.1 List the objectives.

The primary aim of this study is to determine if Nexplanon placed immediately after termination of a second trimester pregnancy vs. 2-4 weeks post-procedure improves use of Nexplanon at 6 months following the pregnancy termination. Secondary objectives include determining the rates of satisfaction, side effects, and repeat pregnancies in each group.

Exploratory objectives:

- To examine the type of insurance plan that women seeking a second trimester surgical abortion, who also desire Nexplanon for contraception, are enrolled in. Additionally we seek to determine if insurance status is a covariate of the primary endpoint.
- To measure the prevalence of lifetime and recent reproductive coercion (RC) and intimate partner violence (IPV) in women seeking second trimester surgical abortion, who also desire Nexplanon for contraception.

2.1.1 List the clinical hypotheses.

- Women who receive Nexplanon immediately post abortion will be significantly more likely to be using the device 6 months after the procedure than those assigned to receive the device 2-4 weeks after the procedure.
- Women in the immediate insertion group will report significantly greater satisfaction, the same or fewer side effects, and fewer repeat pregnancies than those in the control group.
- Women with private health insurance will be significantly more likely to be using the device 6 months after the procedure than those who have public health insurance or no insurance at all.
- Insurance status is a significant covariate in predicting the primary endpoint.
- Women with a history of RC/IPV at the time of enrollment will have greater odds of having a prior abortion compared with women who report no history of RC/IPV.
- Among women randomized to the delayed insertion group, those with a history of RC/IPV at the time of enrollment will be less likely than those without a history of RC/IPV to return to the clinic 2-4 weeks later for Nexplanon insertion.


2.2 Background & Rationale, Significance of Selected Topic & Preliminary Data
	
Nexplanon, an etonogestrel implant, is a safe, highly-effective and well-tolerated method of long-term birth control. In fact, implants are in the top tier of effective contraception (1). Providing women who have had a second trimester termination with the option of an implant could significantly reduce unplanned and undesired future pregnancies. Immediate rather than delayed implant insertion after a termination of pregnancy may be beneficial for several reasons. The most compelling argument is poor post-operative follow up rates. On a national level the percentage of patients that do not return for this visit is about 35-60% (2). Given the poor follow-up rate, failure to utilize the immediate post procedure period to provide patients with effective long-term contraception is likely to lead to a subsequent undesired pregnancy. Additional benefits of post-procedure insertion include greater patient motivation for contraceptive use as well as avoidance of additional discomfort from a second procedure at a later date (4). A recent study by the primary investigator, [name], showed that women randomized to immediate insertion were significantly more likely to have an IUD at 6 months compared to delayed (81.7% vs. 28.4%, p=.003). Relative risk was 11.2 (95% CI 5-26) (5). A similar, observational study by Tocce, et al. showed similar results to immediate vs. delayed placement of post-partum etonogestrel implant among adolescents (6). There are no studies to date in a post-abortion population and this information would help guide management.

2.3 Study Design
	
This is a randomized controlled trial comparing immediate vs. delayed placement of Nexplanon after second trimester abortion procedures. Enrollment will be conducted at Family Planning Associates Medical Group (FPA) in Chicago. This is an independent medical group that is the leading abortion provider in the Chicago area, providing over 1,800 second-trimester abortions per year.
 
[name] successfully conducted a similar study at Parkmed and Bellevue Hospital on immediate vs. delayed IUD placement after second trimester abortion (5).
 
[name], the physician in charge of the study at FPA, is a board certified Obstetrician Gynecologist who completed a Family Planning fellowship, an ACOG member, and the former Director of the Fellowship in Family Planning at the University of Illinois at Chicago.

2.4 Study Flowchart

	Pre-op	Post-op	Immediate*	Delayed*	6 month
Consent/Enrollment	X				
Counseling	X		X	X	
Ultrasound to confirm gestational age	X				
Routine blood work, per clinic protocol (Hct, etc.)	X				
Staff-administered insurance questionnaire	X				
Self-administered RC/IPV questionnaire	X				
Physical Exam	X				
Randomization		X			
Device insertion			X	X	
Implant check-immediately after placement			X	X	
Urine Pregnancy Test				X**	
Directed Physical Exam				X	
Delayed Insertion Questionnaire				X	
Telephone satisfaction Questionnaire					X

* Participants will be randomized to either immediate or delayed insertion.
 ** A urine pregnancy test will be performed on participants who present for delayed insertion of the device outside of the 2-4 week window. Women who test positive for pregnancy will not be able to receive the device. They will be referred for the appropriate medical care.

2.5 Study Procedures

PARTICIPANTS

Eligibility criteria:

Women will be eligible for the study if they are/have:

- 1) 18 years of age and older
- 2) an intrauterine pregnancy ≥ 14 0/7 weeks and ≤ 23 6/7 weeks gestation and desire termination of pregnancy
- 3) desire a Nexplanon for contraception
- 4) able to give informed consent in English
- 5) no contraindications to Nexplanon (based on U.S. CDC Medical Eligibility Criteria for Contraception) or D&E

Exclusion Criteria:

Women will be excluded from the study if they are/have

- 1) unable to give informed consent
- 2) have any of the following medical conditions: active venous thromboembolism, known or suspected sex-steroid sensitive malignancies,

- current hepatic disease with abnormal liver function tests, undiagnosed vaginal bleeding, hypersensitivity to any of the ingredients in Nexplanon
- 3) non-surgical management of pregnancy
 - 4) prior participation in this study
 - 5) breast cancer or a history of breast cancer

INTERVENTIONS

Eligible women seeking abortion services will undergo standard clinical procedures for preoperative evaluation. These include an ultrasound to estimate gestational age; routine blood work; routine abortion counseling and consenting; and routine contraceptive counseling, with the addition of Nexplanon as an option, since the clinic does not currently offer the device except through the study. Women whose pregnancies are confirmed to be in the second trimester and who express that they would like to use Nexplanon for contraception after the abortion, will be told about the study by clinic staff. Interested women will then be further screened for inclusion and exclusion criteria. If eligible for participation, research staff will then review study procedures and the risks and benefits of participation with the patient. Patients will then review and sign the informed consent with an investigator. Once informed consent is obtained, the subject will be assigned a screening number. Additional screening for exclusion criteria will be completed at the time of examination prior to osmotic dilator insertion. Participants will also sign the manufacturer's Nexplanon device consent, as well as a site-specific Nexplanon consent, prior to randomization.

The following information will be recorded in each participant's research chart:

- Contact and demographic information
- Staff-administered Insurance Questionnaire
- Self-administered RC/IPV Questionnaire
- Pregnancy, reproductive, contraceptive, general health histories
- Height and weight
- Results of general appearance exam and other body systems (if indicated)
- Concomitant medications
- Documentation of contraceptive counseling

All participants will undergo termination of pregnancy by dilation and evacuation (D&E) at Family Planning Associates. Eligible participants will complete enrollment before placement of dilators, which is usually performed one day prior to the D&E, but may be the same day, per clinic protocol. Participants will be randomized after the D&E procedure is complete to either "immediate" or "delayed" Nexplanon placement. Insertion of dilators will be performed by either first-clinician [name], P.A., or [name]. All D&Es, as well as all Nexplanon insertions, will be performed by [name]

[name] at FPA. She is trained and approved to place Nexplanon and will place all devices in women enrolled at FPA.

Since randomization occurs after the abortion, both groups will undergo a termination of pregnancy in the exact same manner. Participants in the immediate group will have an etonogestrel rod placed within 15 minutes following the procedure, and while still anesthetized. Participants in the “delayed” placement group will be asked to return to FPA for a post-abortion visit 2-4 weeks following the procedure. Participants in the delayed group will be offered a method of contraception to use in the interim between their procedure and their insertion appointment. At their follow-up visit, an etonogestrel rod will be placed in their arm using standard procedure.

Women randomized to “delayed” insertion will receive one reminder phone call, email, or text message (method of their choosing) about their appointment from the research staff. Attempts will not be made to contact them after a missed appointment.

In the event that participants miss their appointment for Nexplanon placement and still desire the device, they are eligible for placement up to 6 months after their abortion procedure. Under this circumstance, it is the subject’s responsibility to coordinate an appointment with the research office.

All participants will receive a phone call from a research assistant at 6 months to complete a Satisfaction Questionnaire.

Delayed Insertion Visit

The following procedures will be conducted at the delayed insertion visit.

- Review of contact information/emergency contact information
- Review of concomitant medications and contraception since D&E procedure
- Review of adverse events since D&E
- Confirmed continued eligibility to receive Nexplanon
- Review of sexual intercourse history since D&E procedure
- Staff-administered Delayed Insertion Questionnaire
- Collection of vital signs (blood pressure, pulse)
- Directed physical exam
- Insertion of Nexplanon device using standard procedure

Additional procedures to be performed if visit is conducted outside of 2-4 week window

- Urine pregnancy test
- Review of sexual intercourse since LMP

Phone Call (6 month) Procedures

Participants will be contacted by research staff 6 months (+/- 2 weeks) after

	
their abortion procedure. A Satisfaction Questionnaire will be completed during the phone call. Participants will be asked to palpate their implant while on the phone to confirm current use of Nexplanon. Phone calls completed out of window will be documented as a protocol deviation. Those who complete this follow-up will have their addresses re-confirmed and a \$25 gift card will be mailed to them.
 
Comparison Groups and Outcomes Participants who are randomized to have Nexplanon placed immediately post procedure will be compared to participants who were randomized to have Nexplanon placed 2-4 weeks post procedure. The primary outcome will be participants using Nexplanon at 6 months following the procedure. Secondary outcomes will be repeat pregnancy rates, side effects, and contraceptive method satisfaction as assessed by the Satisfaction Questionnaire. Data will also be collected on women who return to have their Nexplanon placed beyond the 2-4 week post-procedure period. Within- and between-group analyses will also be performed to see if insurance status or history of RC/IPV are predictors of the primary or secondary outcomes.

2.6 Study Duration
	
24 months


2.7 Statistical Analysis and Sample Size Justification
	
The data will be analyzed by a contract statistician, [name] at the University of Southern California.
 
STATISTICAL METHODS: The primary outcome to be analyzed is the percentage of women using Nexplanon at the end of 6 months. This analysis will be done with a chi-square test. Secondary outcomes to be analyzed include the proportion of participants using other high or middle tier contraception, pregnancy rates, side effects and satisfaction with the procedure.
 
SAMPLE SIZE: We aim to recruit 120 women seeking termination over 2 years who agree to participate in this study and desire to have Nexplanon as their postpartum contraceptive method. The sample size was calculated based on a power of 0.80 to demonstrate a 20% difference in usage rates of Nexplanon between groups, assuming 40% of women overall are not using Nexplanon six months after their procedure.
 
RANDOMIZATION/SEQUENCE GENERATION/IMPLEMENTATION Prior to randomization allocation of treatment will be unknown by the investigators or the patient. Consent will be obtained prior to the scheduled procedure. However, randomization will occur immediately after the procedure in the operating room, while the patient is still sedated. Sequentially numbered, opaque, sealed envelopes will be placed in the FPA office. An unopened envelope will be placed in the participant’s chart before

the procedure. If the subject changes her mind about participation, the envelope will be returned unopened to the FPA office. Participants will be randomized using a computer-generated table of random numbers. A permuted block design will be used, with a block size of 10. However, since two subjects were recruited at another site that was closed for the study before the completion of follow-up, the first block will be a block of 8.

Blinding:

After randomization, neither the participants nor the physicians will be blinded to the treatment.

Withdrawals, Losses and Deviations:

Every attempt will be made to minimize withdrawal from the study. In the event that a woman does withdraw from the study, the investigators will try to determine the reason for the withdrawal and include this information in the analysis. Participants will be contacted 6 months following the procedure and asked to complete a Satisfaction Questionnaire. Participants will be asked to palpate their device while on the phone. If the device is palpable she will be considered as using Nexplanon at 6 months. In the rare case that the participant cannot palpate the device she will be brought in to FPA for clinician evaluation (unscheduled visit).

Research staff will make at least three attempts to contact participants by phone at 6 months. If these attempts are unsuccessful a certified letter and U.S. mail letter will be sent to the participant's last known address. If the certified letter is returned to the research office unopened, staff will contact the participant's emergency contact provided at enrollment.

This patient population is at high-risk for loss to follow-up. At enrollment participants will give their contact information as well as names and phone numbers of two people who do not live with them who may be able to contact them in case they cannot be reached. To ensure that we reach the 120 sample size we will enroll 150 women since there will be a proportion of women who cannot be reached at the end of the study.

All participants will be compensated \$75 for participation at screening/enrollment. Participants in the delayed group will receive \$15 at their follow-up visit for Nexplanon placement. Finally, all participants will be compensated with a \$25 gift card, delivered by mail, after completing the Satisfaction Questionnaire at 6 months.

Patients who deviate from the protocol will be analyzed according to their allocation group at the time of enrollment (intention-to-treat).

Data Collection/Outcome Measurement

All patients undergoing termination of pregnancy will have a complete history, physical exam and routine labs prior to the procedure. This

	
information will be filled out on a data extraction form following enrollment. Subjects who are enrolled in the study to delayed placement will have an extra visit to place the device. All subjects will be contacted by phone at 6 months to fill out a questionnaire and a satisfaction survey.


2.8 Specific Drug Supply Requirements
	
We are requesting 150 Nexplanon devices to use for the study. All devices will be accounted for and any unused devices will be shipped back to Merck at the end of the study.

2.9 Adverse Experience Reporting
	
Adverse Event (AE)
 
An adverse event (AE) is any untoward or undesirable event experienced by a participant regardless of whether the event is expected or related to the participant’s involvement in the research. Possible adverse events unique to this study include complications from Nexplanon insertion.
 
Serious Adverse Event (SAE)
 
A serious adverse event (SAE) is any untoward medical occurrence or effect involving
 
 ▪ Death ▪ A life-threatening condition (participant at immediate risk of death) ▪ Persistent or significant disability/incapacity ▪ In-patient hospitalization or prolongation of existing hospitalization ▪ A congenital anomaly or birth defect ▪ An important medical event that may jeopardize the participant or may require intervention to prevent one of the outcomes listed above. 
Unanticipated Problems
 
In addition to adverse events as described above, there are events that occur during studies that represent unanticipated problems but are not considered adverse events. In other words, harm to a participant need not occur in order for an event to be an unanticipated problem e.g., laptop with data is stolen.
 
Procedures
 
The Site Investigator, [name], will report AEs, SAEs, and unanticipated problems to the Principal Investigator, [name], to be reviewed and evaluated throughout the study. [name] will decide how to report these according to the guidelines below.
 
All SAEs will be followed until satisfactory resolution or until the PI deems

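### Before the 6-month call, contact details are refreshed only for delayed-arm women who attend for insertion; if that helps tracing, the arm difference would shrink somewhat (minor)

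*Combined protocol and SAP*

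**What the plan says.** All participants supply tracing details before the procedure. Section 2.7 (Withdrawals, Losses and Deviations) states: "At enrollment participants will give their contact information as well as names and phone numbers of two people who do not live with them".

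After that, the arms differ:

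- **Delayed arm, attenders.** The visit list in section 2.5 opens with "Review of contact information/emergency contact information".
- **Delayed arm, all women.** Before the appointment they "will receive one reminder phone call, email, or text message (method of their choosing) about their appointment from the research staff". No check of contact details is described as part of it.
- **Delayed arm, non-attenders.** "Attempts will not be made to contact them after a missed appointment". A woman who still wants the device may arrange placement herself up to 6 months after the abortion.
- **Immediate arm.** The flowchart (2.4) and section 2.5 schedule nothing between insertion on the day of the D&E and the 6-month call.

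At 6 months the tracing rule is common to both arms: "Research staff will make at least three attempts to contact participants by phone at 6 months", then letters, then the emergency contact. Use is established on that call by palpation. The plan also says "Those who complete this follow-up will have their addresses re-confirmed", but that step follows a completed call, so it cannot affect who is reached. Section 2.7 acknowledges the setting: "This patient population is at high-risk for loss to follow-up". It gives no rule for a woman whose 6-month outcome is not obtained.

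**The concern.** In the delayed arm, attending the insertion visit is close to a precondition for using the device at 6 months, because section 2.5 says the clinic supplies it only through the study. The one refresh of contact details therefore goes to almost exactly the women who can be counted as users in that arm. Non-attenders, nearly all non-users, are sought with older details, as is everyone in the immediate arm.

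The tracing rule is the same in both arms, but the phone numbers, addresses and emergency contacts it uses are not equally current. If fresher details help, the chance of observing the outcome depends on the outcome in the delayed arm, through a route that the immediate arm lacks. At stake is a modest distortion of the primary comparison, in a trial that already plans for one woman in five to be unreachable.

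**Working it through.** **Inputs from the documents**

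- Overall non-use of 40% and a 20-point difference (2.7). With 1:1 allocation (assumed; the ratio is not stated) this gives 70% and 50% use: the mean is 60% and the difference 20 points.
- 150 enrolled so that 120 are reached (2.7): 120/150 = 0.80, a planned reach of 80% with no split by arm. The step from 120 to 150 reproduces, since 120/0.80 = 150. Whether 120 is the right target is a separate question, and nothing below depends on it.

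**Assumptions**

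- Base reach of 80% for every woman whose details are not refreshed.
- A gain *d* of 5 or 10 points for delayed-arm users. The documents give no figure for *d*.

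**1. Only reached women analysed**

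Delayed-arm observed use = 0.50(0.80 + d) / [0.50(0.80 + d) + 0.50 × 0.80]

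| d | Delayed-arm observed use | Gap from 70% | Delayed-arm reach |
|---|---|---|---|
| 0 | 0.400/0.800 = 50.0% | 20.0 | 80.0% |
| 0.05 | 0.425/0.825 = 51.5% | 18.5 | 82.5% |
| 0.10 | 0.450/0.850 = 52.9% | 17.1 | 85.0% |

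**2. Unreached women counted as non-users**

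Immediate arm: 0.70 × 0.80 = 56.0%. Delayed arm: 0.50(0.80 + d) = 40.0%, 42.5% or 45.0%. The gaps are 16.0, 13.5 and 11.0 points. The fall from 20 to 16.0 comes from the counting rule itself, which the plan does not state. The refresh accounts for the further 2.5 or 5.0 points.

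**3. Refresh applied to all who return**

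Some women return, receive the device and stop using it before 6 months; their details are refreshed too. With return share R, observed use = 0.50(0.80 + d) / [R(0.80 + d) + (1 − R)0.80]. Take R = 0.55, within the 40–65% return implied by the 35–60% national non-return in 2.2, and R = 0.50/0.70 = 0.714, which assumes that recipients in both arms continue at 70%.

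- d = 0.05: 0.425/0.8275 = 51.4% and 0.425/0.8357 = 50.9%; gaps 18.6 and 19.1.
- d = 0.10: 0.450/0.855 = 52.6% and 0.450/0.8714 = 51.6%; gaps 17.4 and 18.4.

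The direction is the same as in step 1 and the effect slightly smaller.

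**4. Is the net direction fixed?**

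Suppose immediate-arm users are reached at 85% and non-users at 68%, so that overall reach is 0.595 + 0.204 = 79.9%. Observed immediate-arm use is 0.595/0.799 = 74.5%. Against the delayed-arm values in step 3 with R = 0.714, the gap is 23.6 (d = 0.05) or 22.8 (d = 0.10), above the true 20. The direction is not fixed.

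**The case against.** The strongest reply is that the refresh may do little. It normally happens 2–4 weeks after the D&E and leaves about five months for details to go out of date again. Both arms also give two outside contacts and receive the same calls, letters and emergency-contact tracing. This stands as a limit on size: with d = 0 there is no bias. It does not remove the asymmetry, because all those steps draw on the details that only attenders have reviewed, and a woman who returns late may have hers updated shortly before the outcome call.

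The effect is also small against sampling error. With 60 reached per arm, the standard error of the difference is √(0.70 × 0.30/60 + 0.50 × 0.50/60) = 8.8 points, against a shift of 1.5 to 2.9 among reached women. At the 81.7% and 28.4% seen in the IUD trial cited in 2.2, a 10-point gain gives delayed-arm use of 0.2556/0.8284 = 30.9% and moves the gap from 53.3 to 50.8. That stands too, and is why the priority is minor.

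Three stronger readings are tempting, and the documents support none of them:

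- *The primary comparison is biased toward zero.* This requires that the refresh improves reach, for which there is no figure, and that no outcome-linked loss in the immediate arm offsets it.
- *The gap could fall to 16.9 or 13.8 points.* Those values need delayed-arm non-users to be reached at only 75% or 70%, with users at 85% or 90%. A refresh can raise attenders' reach; it cannot lower that of non-attenders, who are traced with the same kind of details as the immediate arm.
- *Comparing total follow-up by arm would show nothing.* Under this mechanism delayed-arm reach would be 82.5% or 85% against 80%, so the imbalance would appear in that comparison.

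**Conclusion.** The asymmetry is in the plan: before the outcome call, only delayed-arm attenders have their contact details reviewed, and attendance is closely tied to the primary outcome in that arm. The consequence is conditional. If the review raises 6-month reach by 5 or 10 points, the expected difference among reached women loses about 1.5 or 2.9 of its 20 points (somewhat less when women who return and later stop are allowed for). If unreached women count as non-users, it loses 2.5 or 5.0 points beyond the effect of that rule. These figures rest on 70% and 50% true use, 80% base reach and assumed gains; the documents state no reach rates. The net bias over both arms could be smaller, nil or in the other direction. This is a minor point, worth acting on because the remedy is cheap. The lack of a missing-outcome rule is the more basic gap.

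**What to change.** 1. Add a contact and emergency-contact check to the reminder that every delayed-arm woman already receives. It goes out before the appointment, so the rule on no contact after a missed visit is untouched.
2. Send immediate-arm women a matching check, limited to contact details, at the same interval after the D&E and by the channel they choose.
3. Report 6-month reach by arm and, in the delayed arm, by whether the woman returned.
4. As a sensitivity analysis, use study insertion records to classify unreached delayed-arm women who never received a study device as non-users. This assumes that they did not obtain one elsewhere. It adds known non-users while unreached recipients stay missing, so it can overshoot: with R = 0.714 and d = 0.10, delayed-arm use is 0.450/(0.6429 + 0.2857) = 48.5% and the gap 21.5. Showing next to it the share given a device times use among reached recipients (0.714 × 0.70 = 50%) restores the 20-point gap, if users and non-users among recipients are equally reachable.

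**Cost.** A small amendment, one added line in an existing reminder, and one extra contact for about 150/2 = 75 immediate-arm women. The check reduces the link between reach and return but does not remove it: it travels to existing details, and the women who answer are plausibly those who will attend.

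### Does the secondary-outcome list in section 2.7 name the wrong satisfaction outcome and leave 'the same' side effects untestable?

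*Combined protocol and SAP*

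**What the plan says.** All references are to the combined protocol and SAP.

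- **Section 2.1.1** (clinical hypotheses): "Women in the immediate insertion group will report significantly greater satisfaction, the same or fewer side effects, and fewer repeat pregnancies" than the control group. Section 2.1 states the matching objective more modestly, as determining rates of these outcomes in each group.
- **Section 2.5** (Comparison Groups and Outcomes): "Secondary outcomes will be repeat pregnancy rates, side effects, and contraceptive method satisfaction as assessed by the Satisfaction Questionnaire". The instrument goes to both arms: "All participants will receive a phone call from a research assistant at 6 months to complete a Satisfaction Questionnaire".
- **Section 2.7** (Statistical Methods): the chi-square test is stated for the primary outcome only. The secondary outcomes are said to include "the proportion of participants using other high or middle tier contraception", followed by "pregnancy rates, side effects and satisfaction with the procedure". No test, estimate, interval or margin is given for any of them.
- **Section 2.7** (sample size; withdrawals): 120 women are wanted for analysis and 150 are to be enrolled, with analysis by allocated group.

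**The concern.** There are two separate worries.

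**Satisfaction.** Section 2.5 attaches satisfaction to the contraceptive method and 2.7 attaches it to the procedure. In this document that noun phrase normally means the abortion, as in "randomization will occur immediately after the procedure in the operating room". The abortion cannot differ by arm, because "both groups will undergo a termination of pregnancy in the exact same manner". Read that way, 2.7 would compare something allocation cannot have altered, and would not address the hypothesis of greater satisfaction. If insertion is meant instead, as in the background's "avoidance of additional discomfort from a second procedure at a later date", delayed-arm women who never return have nothing to rate. The comparison would then be limited to women selected after randomisation.

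**Side effects.** A prediction of no more side effects, with no stated analysis, invites a familiar error: a non-significant test in a small trial reported as evidence of no difference. A real excess in the immediate arm could be passed over in this way.

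**Working it through.** **1. The satisfaction label.** No arithmetic applies, so the texts are compared.

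- Apart from the disputed entry, the exact phrase 'the procedure' occurs 10 times in sections 2.1.1 to 2.7: three in 2.1.1, three in 2.5 and four in 2.7. All 10 mean the abortion.
- The bare word is used more loosely. Section 2.5 twice uses it for the standard way of inserting the implant, and section 2.2 calls a later insertion a second procedure. The count shows the usual sense, not what the author of the 2.7 list meant.
- Section 2.5 names the outcome together with its instrument. Section 2.7 names no instrument in its list and introduces that list as an open one, so it does not withdraw the 2.5 outcome.
- The Satisfaction Questionnaire is the only satisfaction instrument given a name, although the data-collection paragraph of 2.7 mentions a satisfaction survey alongside a questionnaire. Its items are not in the documents. If it yields one score, only the label is wrong. If it has separate items for method and procedure, 2.5 already says which is the outcome.

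**2. Precision for side effects.** The plan gives no side-effect rate and no sample-size figure for this outcome, so there is no stated figure to reproduce. Its 120 belongs to the primary outcome. That 120 does not follow from its own inputs: 50% against 70%, two-sided 5%, 80% power gives [1.96√(2×0.6×0.4) + 0.842√(0.25+0.21)]² / 0.2² ≈ 93 per arm, or 186 in total. That is a separate matter. Here 120 and 150 serve only as numbers of women.

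Inputs:
- 60 per arm (120/2) or 75 per arm (150/2); 1:1 allocation is assumed, as the ratio is not stated.
- Two-sided 5% level, assumed.
- Binary side-effect endpoint with rates from 10% to 50%, assumed.

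95% half-width for a difference when both arms have rate p: 1.96 × √(2p(1−p)/n). At p = 10% and n = 60 this is 1.96 × √0.003 = 0.107.

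| Rate | 60 per arm | 75 per arm |
|---|---|---|
| 10% | ±10.7 points | ±9.6 points |
| 20% | ±14.3 | ±12.8 |
| 30% | ±16.4 | ±14.7 |
| 50% | ±17.9 | ±16.0 |

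Probability that an uncorrected chi-square test is non-significant when the immediate arm truly has 10 points more side effects (exact binomial enumeration):

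| True rates | 60 per arm | 75 per arm |
|---|---|---|
| 20% vs 10% | 67% | 59% |
| 30% vs 20% | 75% | 71% |
| 50% vs 40% | 80% | 75% |

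A non-significant p-value alone is therefore weak evidence of sameness.

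**3. Does that make the hypothesis unsupportable?** The claim is the same *or fewer*, so what matters is the upper limit for an excess in the immediate arm. Examples with 60 per arm, immediate arm first:

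- 24/60 vs 18/60: difference +10 points; standard error √(0.4×0.6/60 + 0.3×0.7/60) = 0.0866; 95% CI −7 to +27; p = 0.25. A large excess is not excluded.
- 18/60 vs 24/60: same p = 0.25; 95% CI −27 to +7. A 10-point excess is excluded.
- 6/60 vs 12/60: standard error √(0.1×0.9/60 + 0.2×0.8/60) = 0.0645; 95% CI −23 to +3; p = 0.125. Again excluded.

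The same p-value can accompany either conclusion; the interval separates them. With equal true rates, the chance that the upper limit falls below a margin m is Φ(m/√(2p(1−p)/60) − 1.96). For m = 10 points this is 0.45 at a 10% rate and 0.19 at 50%. For m = 20 points at a 10% rate it is 0.955, and for m = 25 points at a 50% rate it is 0.78. Whether this size suffices depends on the margin.

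**The case for a change.** The best case for acting is that 2.7 is the section the contract statistician will work from, that the document's own usage points to the abortion, and that nothing written prevents either the wrong satisfaction item being analysed or a non-significant side-effect test being called sameness. The repair would cost one phrase and one interval, and settling it beforehand removes any choice made after seeing results.

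The factual core stands: the two labels differ, and the side-effect analysis is unwritten. The consequence is not shown. Nothing in the documents indicates that the questionnaire would give a different answer under either label, and the feared reading of non-significance appears nowhere in the plan.

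A further argument is that method satisfaction is undefined for women using no method, so a rule for them is needed. If 80% of users are satisfied in both arms and no-method use is 10% (immediate) against 20% (delayed), a users-only analysis gives 80% vs 80%. Keeping every woman reached gives 0.80 × 0.90 = 72% against 0.80 × 0.80 = 64%, a gap of 8 points. But this does not measure the mismatch between method and procedure, and all the inputs are assumed. The whole gap comes from method use, so the rule would carry much of the primary outcome into the satisfaction result. It is a debatable trade-off, not a correction.

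**Conclusion.** No change to the plan follows. The satisfaction entry in 2.7 is probably a clerical slip. Section 2.5 identifies the outcome and its questionnaire, and an analyst would use that; aligning the label is housekeeping. This rests on the questionnaire measuring what 2.5 says it measures, which the documents do not let one check.

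The side-effect point is a missing detail that ordinary practice fills: report the difference by allocated arm with its 95% interval and judge the hypothesis by the upper limit for an excess. The imprecision is real: about ±11 to ±18 points at 60 per arm, with a true 10-point excess non-significant about 67% to 80% of the time. These figures rest on assumed rates, 1:1 allocation, a binary endpoint and a two-sided 5% level. They limit what the trial can say about side effects, but they do not show an error in the planned analysis. It is also too strong to say that a non-significant result can never support the hypothesis, as 18/60 against 24/60 shows. The primary outcome is untouched.
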